7.2. Discussion of Study Design

A double-blind, randomized, placebo-controlled study is considered a gold-standard for conducting any interventional and dose-finding study. A sample size of 50 patients per treatment arm is also adequate to get robust outcome data for a comparison among doses and with placebo.

Psoriasis is a chronic condition requiring long-term therapy. Primary efficacy assessments of psoriasis clinical trials are usually performed at 12 or 16 weeks after initiation of study treatment. Because of the initial titration period of up to 2 weeks duration, a treatment duration of 16 weeks, with the primary endpoint being evaluated at this time point is, therefore, considered the optimal strategy for this study. Primary evaluations of apremilast, the only PDE4 inhibitor currently approved for psoriasis treatment, were also conducted at Week 16. A 16-week Treatment Period was also deemed acceptable for the placebo arm because psoriasis is not a life-threatening disease warranting immediate treatment.

Besides the usual psoriasis assessments including the PASI, the IGA, and the BSA, the effects of study treatment on nail and scalp psoriasis that represent location of disease more refractory to treatment will be explored. In patients with PsA, any potential effect on will be also assessed. A number of patient-reported outcome (PROs) will be administered to explore the patient's perception of his or her condition and the related QoL, as recommended by regulatory agencies. This comprehensive evaluation of the psoriatic condition of patients will contribute to the selection of the most suitable dose(s) for the Phase 3 clinical program.

^{*}To maintain the study blind.

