9.3.1. Titration

Titration of oral apremilast was shown to improve the GI tolerance and overall acceptability of the drug (Zerilli 2015). Similarly, a slow increase in orismilast dose was associated with less GI side effects when compared with a rapid increase. Consistent with this approach, this study will titrate the study treatment dose over a period of maximum 2 weeks (see Table 2).

If tolerability issues arise during the treatment up-titration and/or during maintenance period, the following treatment pauses are allowed only if instructed by the Investigator:

- First day: The Investigator is informed of the tolerability issue; thus, the evening dose can be skipped.
- Second day: Morning dose can be skipped. The patient must take the evening dose.
- Third day: Similar to Day 2, morning dose can be skipped. The patient must take the evening dose.
- Fourth day: BID daily dosing regimen is reintroduced.

The aforementioned treatment pauses do not impact calculation of dosing days and duration of titration is not prolonged. Treatment pauses will be captured in the eCRFs. This titration will not break the blind as all patients will receive 2 of indistinguishable orismilast or placebo tablets BID.

Table 2. Dose Titration Schedule

Arm	Day 1	Da	y 2	Da	у 3	Da	y 4	Da	y 5	Da	y 6	Da	y 7	Da	ıy 8	Da	y 9	Day	y 10	Day	/ 11	Day	y 12	Day	/ 13	Day	14	From I	Day 15
20 mg BID	10	10	10	10	10	10	10	10	20	10	20	10	20	20	20	20	20	20	20	20	20	20	20	20	20	20	20	20	20
30 mg BID	10	10	10	10	20	20	20	20	20	20	30	20	30	20	30	30	30	30	30	30	30	30	30	30	30	30	30	30	30
40 mg BID	10	10	10	10	20	20	20	20	20	20	30	20	30	20	30	30	30	30	30	30	30	30	40	30	40	30	40	40	40
Placebo	Р	Р	Р	Р	Р	Р	Р	Р	Р	Р	Р	Р	Р	Р	Р	Р	Р	Р	Р	Р	P	Р	Р	Р	Р	Р	Р	Р	P

Abbreviation: BID, twice daily

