## 4. Study Details/Design

### 4.1. Brief Description

This multicenter, randomized, double-blind, placebo-controlled, parallel-group, Phase 2b dose-ranging study is designed to assess the efficacy and safety of modified-release orismilast compared with placebo in adult patients with moderate-to-severe plaque-type psoriasis. Efficacy and safety endpoints will be evaluated to select an appropriate orismilast dose for subsequent Phase 3 studies. The study will be conducted in approximately 40 centers in Europe (Germany, Poland, UK) and US.

After a Screening visit up to 28 days before Baseline, approximately 200 patients will be assigned randomly in a 1:1:1:1 ratio to receive 1 of the 3 orismilast doses (20 mg, 30 mg, or 40 mg) or placebo twice daily (BID) for 16 weeks, with a 4-week Follow-up visit. Administration will begin at Baseline with a dose titration period of up to 14 days (for the orismilast arm only). The maximum duration of study participation is approximately 24 weeks.

Patients will be seen at the site on Screening, Baseline (Day 1), and Weeks 1, 2, 4, 8, 12, 16 (End-of-Treatment [EOT] visit), and 20 (Follow-up visit, 4 weeks after treatment completion or discontinuation). Visits at Weeks 1 and 2 could be conducted via a telemedicine procedure at Investigator's discretion.

At Baseline and each visit from Week 4 onwards, Psoriasis Activity and Severity Index (PASI), body surface area (BSA), Investigator Global Assessment (IGA), and Psoriasis Symptoms Scale (PSS) will be assessed. Quality of life will be assessed by administration of Dermatology Life Quality Index (DLQI) at Baseline and at Weeks 16 and 20 visits. Additional efficacy parameters include: a Scalp-specific Investigator Global Assessment (ss-IGA), a nail psoriasis Physician Global Assessment (PGA-F), and

These parameters will be assessed at Baseline and Weeks 16 and 20. Safety evaluations include adverse events (AEs), laboratory and vital sign assessments, physical examinations as well as mood change evaluation by patient (Hospital Anxiety and Depression Scale [HADS]) and suicidal ideation evaluation by Investigator (Columbia-Suicide Severity Rating Scale[C-SSRS]). A panel of cardiovascular risk factors will be assessed at Baseline and Week 16.

Before administration of the study drug at Baseline and on Weeks 4, 8, and 16, blood will be collected for orismilast concentration determination. In addition, [REDACTED]

[figure not shown]
[REDACTED] See [REDACTED]

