- An overall summary of the number of events and number and percentage of patients reporting TEAEs, related TEAEs (TEAEs recorded as “Relationship to study drug” = “Possibly” or “Probably” or “Definitely”), serious TEAEs (TESAEs), TEAEs resulting in death, TEAEs of special interest, TEAEs leading to study drug discontinuation, TESAEs leading to study drug discontinuation, TEAEs by relationship and TEAEs by toxicity grade starting within the dose titration period (initial 3 weeks)

This document is confidential.

- TEAEs overall by system organ class and preferred term starting within the dose titration period (initial 3 weeks)
- TEAEs by maximum toxicity grade, overall and by system organ class and preferred term;
- TEAEs by toxicity grade, overall and by system organ class and preferred term;
- TEAEs by maximum relationship to study medication, overall and by system organ class and preferred term;
- TEAEs by relationship to study medication, overall and by system organ class and preferred term;
- TESAEs, overall and by system organ class and preferred term;
- TESAEs by maximum toxicity grade, overall and by system organ class and preferred term;
- TESAEs by toxicity grade, overall and by system organ class and preferred term;
- TESAEs by maximum relationship to study medication, overall and by system organ class and preferred term;
- TESAEs by relationship to study medication, overall and by system organ class and preferred term;
- TEAEs leading to study drug discontinuation, overall and by system organ class and preferred term;
- TEAEs leading to death, overall and by system organ class and preferred term;
- TEAEs of special interest, overall and by system organ class and preferred term;
- AEs starting in the 4-week Follow-up period overall by system organ class and preferred term;
- SAEs starting in the 4-week Follow-up period overall and by system organ class and preferred term;

Only TEAEs will be included in the summary tables, however separate listings for treatment-emergent AEs, non-treatment-emergent AEs, AEs starting within the dose titration period (initial 3 weeks) and AEs starting in the 4-week Follow-up period will be generated. Additional listings will be provided for deaths, AESIs, serious AEs and Adverse Events Leading to Study Drug Discontinuation.

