	14.3.1.8	Overall Summary of Treatment Emergent Adverse Events (TEAEs) Starting Within the Dose Titration Period (initial 3 weeks)	Safety Population
	14.3.1.9	Treatment Emergent Adverse Events (TEAEs) by System Organ Class and Preferred Term Starting Within the Dose Titration Period (initial 3 weeks)	Safety Population
	14.3.1.10	Summary of Treatment Emergent Adverse Events (TEAEs) by System Organ Class, Preferred Term and Maximum Toxicity Grade	Safety Population
	14.3.1.11	Treatment Emergent Adverse Events (TEAEs) by System Organ Class, Preferred Term and Toxicity Grade	Safety Population
	14.3.1.12	Treatment Emergent Serious Adverse Events (TESAEs) by System Organ Class, Preferred Term and Maximum Relationship	Safety Population
	14.3.1.13	Treatment Emergent Serious Adverse Events (TESAEs) by System Organ Class, Preferred Term and Relationship	Safety Population

This document is confidential.

Header	Table Number	Name	Analysis Population
	14.3.1.14	Treatment-Emergent Non-Serious Adverse Events by System Organ Class and Preferred Term	Safety Population
	14.3.1.15	Treatment-Emergent Adverse Events Leading to Study Drug Discontinuation by System Organ Class and Preferred Term	Safety Population
	14.3.1.16	Treatment-Emergent Adverse Events Leading to Death by System Organ Class and Preferred Term	Safety Population
	14.3.1.17	Treatment-Emergent Adverse Events of Special Interest by System Organ Class and Preferred Term	Safety Population
	14.3.1.18	Adverse Events Starting in the 4-week Follow-up Period by System Organ Class and Preferred Term	Safety Population
	14.3.1.19	Serious Adverse Events Starting in the 4-week Follow-up Period by System Organ Class and Preferred Term	Safety Population
14.3.2		Listings of Deaths, Other Serious and Certain Other Significant Adverse Events	
	14.3.2.1	Listing of Deaths	Safety Population
	14.3.2.2	Listing of Adverse Events of Special Interest	Safety Population
	14.3.2.3	Listing of Serious Adverse Events	Safety Population
	14.3.2.4	Listing of Adverse Events Leading to Study Drug Discontinuation	Safety Population
14.3.3	Not to be used for any Tables	Narratives of Deaths, Other Serious and Certain Other Significant Adverse Events (NOTE: this section is for Medical Writing narratives only, normally not completed by [REDACTED] Biostatistics. No tables should go here. Nevertheless, the section is kept and a note should indicate the responsible party).	
14.3.4		Laboratory, Vital Signs, and Physical Examination Changes	

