	16.2.6.3.5	Exploratory Endpoint: Cardiovascular Risk Factors - Baseline and Week 16	Randomized Population
	16.2.6.3.6	Exploratory Endpoint: PK Levels of Orismilast and Metabolites	Randomized Population
	16.2.6.3.7	[REDACTED]	Randomized Population
16.2.7		Adverse Event Listings	
	16.2.7.1	Treatment-Emergent Adverse Events	Randomized Population
	16.2.7.2	Non-Treatment-Emergent Adverse Events	Randomized Population
	16.2.7.3	Adverse Events Starting Within the Dose Titration Period (initial 3 weeks)	Randomized Population
	16.2.7.4	Adverse Events Starting in the 4-week Follow-up Period	Randomized Population
16.2.8		Listing of individual laboratory measurements by patient	
	16.2.8.1	Clinical Laboratory Data	
	16.2.8.1.1	Clinical Chemistry	Randomized Population
	16.2.8.1.2	Hematology	Randomized Population
	16.2.8.1.3	Urinalysis	Randomized Population
	16.2.8.1.4	Serology	Randomized Population
	16.2.8.1.5	Pregnancy Tests	Randomized Population
	16.2.8.2	Other Safety Data	
	16.2.8.2.1	Vital Signs	Randomized Population
	16.2.8.2.2	Electrocardiogram (ECG)	Randomized Population
	16.2.8.2.3	ECG Overall Evaluation	Randomized Population
	16.2.8.2.4	Physical Examination	Randomized Population
	16.2.8.2.5	Hospital Anxiety and Depression Scale (HADS)	Randomized Population
	16.2.8.2.6	Patients with Suicidal Ideation, Suicidal Behavior, or Self-Injurious Behavior without Suicidal Intent Based on the C-SSRS	Randomized Population

This document is confidential.

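### The SAP's titration-period adverse event outputs cover three weeks, although titration is scheduled to end by Day 14 in every group

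*SAP*

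**What the plan says.** Three weeks appears in these places:

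- SAP 12.1 equates the titration period with the first three weeks in two table bullets and again in the sentence on listings. One bullet reads "TEAEs overall by system organ class and preferred term starting within the dose titration period (initial 3 weeks".
- SAP 18, Table 14.3.1.8: "Overall Summary of Treatment Emergent Adverse Events (TEAEs) Starting Within the Dose Titration Period (initial 3 weeks".
- SAP 18, Table 14.3.1.9: "Treatment Emergent Adverse Events (TEAEs) by System Organ Class and Preferred Term Starting Within the Dose Titration Period (initial 3 weeks".
- SAP 20, Listing 16.2.7.3: "Adverse Events Starting Within the Dose Titration Period (initial 3 weeks".

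Two weeks appears in these places:

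- SAP 4.1: "Administration will begin at Baseline with a dose titration period of up to 14 days (for the orismilast arm only".
- Protocol 7.2: "Because of the initial titration period of up to 2 weeks duration".
- Protocol 9.3.1: "this study will titrate the study treatment dose over a period of maximum 2 weeks". On permitted interruptions the same section adds that "treatment pauses do not impact calculation of dosing days and duration of titration is not prolonged".
- Protocol Table 2 shows all three orismilast groups at target dose, morning and evening, from Day 15.

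SAP 8.8 and Table 14.1.5.2 also summarise compliance for the titration period, but give no length for it.

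**The concern.** The two lengths cannot both describe the same period. A programmer who follows SAP 12.1 will put every TEAE with onset on Days 15-21 into tables headed as titration, although no group is scheduled to be titrating then.

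The label matters because of how these tables will be read. Protocol 5.3 expects gastrointestinal effects mainly when therapy starts and relies on titration to reduce them. The secondary objective is to choose the Phase 3 dose on benefit and risk. The titration tables are the natural place to judge whether the up-titration is tolerated. The extra week also means something different for each dose: it is the first week of full dosing at 40 mg, whereas 20 and 30 mg reached full dosing on Days 8 and 9.

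The compliance table has a related gap. With 14 and 21 days both in the SAP and none stated for Table 14.1.5.2, it could be built on a different window from the adverse event tables.

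**Working it through.** **Inputs.** Protocol Table 2 gives one evening intake on Day 1, two intakes a day on Days 2-14, and the maintenance dose from Day 15. The SAP window is 3 × 7 = 21 days.

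**Step 1: reproduce the two-week figure.** For each group, find the last intake below target and the first day from which every intake is at target.

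| Group | Last below-target intake | First day at full twice-daily dose |
|---|---|---|
| 20 mg | Day 7, morning | Day 8 |
| 30 mg | Day 8, morning | Day 9 |
| 40 mg | Day 14, morning | Day 15 |

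The latest is Day 14, which agrees with SAP 4.1 and protocol 7.2 and 9.3.1. Pauses do not move it.

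**Step 2: size of the excess.** 21 − 14 = 7 days, one third of the window.

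Scheduled intakes:

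- Days 1-21: 1 + 2 × 20 = 41
- Days 1-14: 1 + 2 × 13 = 27
- Days 15-21: 41 − 27 = 14, and 14/41 = 34%, the same in every group

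**Step 3: full twice-daily dosing inside each window.** The count is 2 × (last day of window − first full-dose day + 1).

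| Group | Days 1-21 | Days 1-14 |
|---|---|---|
| 20 mg | 2 × 14 = 28 of 41 (68%) | 2 × 7 = 14 of 27 (52%) |
| 30 mg | 2 × 13 = 26 of 41 (63%) | 2 × 6 = 12 of 27 (44%) |
| 40 mg | 2 × 7 = 14 of 41 (34%) | 0 of 27 |

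A common 14-day window removes the week in which nobody titrates. It does not make the window pure titration for 20 and 30 mg.

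**Step 4: what a 14-day window leaves out.** In the 40 mg group the 40 mg dose is first taken on the evenings of Days 12, 13 and 14, which is 3 intakes. By Day 21 there are 3 + 14 = 17. So 14 of those 17 lie after Day 14, and the morning dose first rises from 30 to 40 mg on Day 15. If the window is cut to 14 days and nothing is added, most early exposure to 40 mg drops out of the early-period table.

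**Step 5: who can have a TEAE on Days 15-21.** SAP 12.1 counts events up to 7 days after the last dose. A patient who stops on Day 8 is covered to Day 15, and one who stops on Day 14 is covered to Day 21. Patients who stop on Days 8-14 can therefore still contribute events after Day 14.

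**The case against.** The best defence is that little is at stake. Both table titles and the listing title print the three weeks, so a careful reader sees the actual window. The listing carries no summary to distort. SAP 12 makes all safety analyses descriptive, and the whole-period tables by treatment group are unaffected. This stands, and it sets the severity.

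A second defence is that the third week is a deliberate margin to catch reactions to the last dose step. Clinically that is reasonable, because the morning dose at 40 mg rises only on Day 15. But neither document says so, and a margin would call for a different title.

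A third is that protocol 15 lets the SAP prevail over the protocol. That rule cannot choose between two values that are both in the SAP. The silence of SAP 14 adds little either way, since protocol 15.4 plans no titration-period table from which to depart.

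Stronger readings are tempting, and the documents do not support them:

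- **That Day 15-21 events belong to maintenance dosing.** At 40 mg, early events in that week may be reactions to the last up-titration step. The schedule shows what was due to be taken, not what caused an event.
- **That the longer window will make 40 mg look worse by some stated amount.** No event rates by study day are given, so neither the direction nor the size of any shift can be calculated.
- **That the titration compliance figures are wrong.** Table 14.1.5.2 has no stated window, SAP 4.1 supplies 14 days, and the table shells are a separate document. The 80% compliance limit in SAP 6.5 applies to the whole treatment period or its last 4 weeks, not to titration.
- **That the three weeks is a leftover from a superseded protocol.** The amendment log makes this plausible, but the contradiction rests on current text alone.

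**Conclusion.** The inconsistency is real and can be checked from the current text. The SAP's adverse event outputs define titration as Days 1-21, whereas SAP 4.1, the protocol and the dose schedule end it by Day 14. Seven of 21 days, and 14 of 41 scheduled intakes, carry a titration label when no group is scheduled to titrate.

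Severity is minor. The effect is on how a descriptive table is labelled and read. No test, efficacy result or whole-period TEAE count changes, and the whole-period tables by group remain a valid randomised comparison of the regimens.

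The conclusion rests on scheduled dosing in Table 2, and on the table shells, which were not available, not redefining the window.

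**What to change.** 1. Set the titration window to study Days 1-14 in SAP 12.1 (both bullets and the listing sentence), Tables 14.3.1.8 and 14.3.1.9 and Listing 16.2.7.3. Use the study-day definition in SAP 7.2. State the same window for Table 14.1.5.2.
2. Add a footnote that 20 and 30 mg reach full twice-daily dose on Day 8 and Day 9, and that 40 mg twice daily starts on Day 15, so events soon after Day 14 may still reflect the last up-titration step.
3. Add a companion table, by system organ class and preferred term, of TEAEs starting from Day 15. Use the full safety population and the denominator already set in SAP 12.1. Restricting it to patients dosed on or after Day 15 would lose events from patients who stopped on Days 8-14 from both period tables, and early intolerance is what a benefit/risk reading needs to see.
4. If the sponsor wants to keep 21 days, retitle those outputs as *first 3 weeks of treatment*, without calling them the titration period.

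The cost is a wording change in a few places, one stated window for compliance and one extra descriptive table. No new data are needed, because protocol 12.9.1 already requires onset dates. Step 1 should not be made without step 3, since Days 1-14 hold only 3 of the 17 intakes of 40 mg taken by Day 21. With the full-population denominator, percentages in the Day 15 table include patients no longer on treatment; a footnote should say so.

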8.4. Study Withdrawal, Removal, and Replacement of Patients

If a patient discontinues study treatment and is withdrawn from the study for any reason, the study site must immediately notify the medical monitor. The date and the reason for study discontinuation must be recorded on the electronic case report form (eCRF). Patients who complete or discontinue early from the study will be asked to return to the study site within 4 weeks of the last administration of study drug to complete EOT assessments as indicated in the

Schedule of Assessments (Table 4). If the study treatment is permanently discontinued, the patient will remain in the study to be evaluated for safety.

In the event that a patient discontinues prematurely from the study because of a TEAE or serious TEAE assessed as \geq Grade 3 (\geq Grade 2 for the system organ class [SOC] of cardiac disorders) according to Common Terminology Criteria for Adverse Events version 5 (CTCAE v 5), the TEAE or serious TEAE will be followed up until it resolves (returns to normal or Baseline values) or stabilizes, or until it is judged by the Investigator to no longer be clinically significant.

Once a patient is withdrawn from the study, the patient cannot reenter the study.

A patient may voluntarily withdraw or be withdrawn from the study at any time for reasons including, but not limited to, the following:

- unacceptable toxicity or AE
- patient's withdrawal of consent: at any time, a patient's participation in the study may be terminated at his/her request or on the basis of the Investigator's clinical judgment. The reason for patient withdrawal will be noted on the eCRF.
- intercurrent illness: a condition, injury, or disease unrelated to the primary diagnosis that became apparent during treatment and necessitated the patient's termination from the study
- general or specific changes in the patient's condition that renders him/her ineligible for further treatment according to the inclusion/exclusion criteria
- patient fails to adhere to the protocol requirements (eg, drug noncompliance, failure to return for defined number of visits)
- lost to Follow up: the patient stopped coming for visits, and study personnel were unable to contact the patient
- pregnancy, as indicated in Section 12.9.6.

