12.9.4. Serious Adverse Event Reporting

An SAE occurring from the time informed consent is obtained, during the study, or within 30 days of stopping the treatment must be reported to Health Safety and Pharmacovigilance group and will be communicated to the Sponsor. Any such SAE due to any cause, whether or not related to the study drug, must be reported immediately, and under no circumstances later than

Safety and Pharmacovigilance

• Safety and Pharmacovigilance email address:

If the Investigator contacts the Safety and Pharmacovigilance group by telephone, then a written report must follow within 24 hours and is to include a full description of the event and sequelae in the format detailed in the SAE reporting form.

The event must also be recorded on the standard AE eCRF. Preliminary reports of SAEs must be followed up by detailed descriptions later on, including clear and anonymized photocopies of hospital case reports, consultant reports, autopsy reports, and other documents when requested and applicable. SAE reports must be made whether or not the Investigator considers the event to be related to the investigational drug.

Appropriate remedial measures should be taken to treat the SAE, and the response should be recorded. Clinical, laboratory, and diagnostic measures should be employed as needed to determine the etiology of the problem. The Investigator must report all additional Follow-up evaluations to Safety and Pharmacovigilance group within 24 hours of becoming aware of the additional information or as soon as is practicable. All SAEs will be followed up until the Investigator and Sponsor agree the event is satisfactorily resolved.

Any SAE that is not resolved by the end of the study or upon discontinuation of the patient's participation in the study is to be followed up until it either resolves, stabilizes, returns to Baseline values (if a Baseline value is available), or is shown to not be attributable to the study drug or procedures.

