### 6.2. Safety Population

The safety population will include all randomized patients who receive at least 1 dose of the study drug. The treatment group assignment in this population will be defined by the treatment actually received. This population will be used for the analysis of safety.

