## 8. Demographic, Other Baseline Characteristics and Medication

### 8.1. Patient Disposition and Withdrawals

Listings of treatment assignments, including the subject's identification, date of randomization, and assignment to treatment, will be presented.

The following frequencies (number and percent) will be displayed for all patients in the screened population: patients screened, patients randomized, screen failures, and reasons for screen failure.

The analysis populations will be summarized with counts and percentages by treatment. This table will include the following: number of patients in screened population, patients in safety population, reasons for exclusion from the safety population, patients in Intent-to-Treat population, reasons for exclusion from the Intent-to-Treat population, patients in Per-Protocol population, and reasons for exclusion from the Per-Protocol population.

The following frequencies (number and percent) will be displayed for all patients in the randomized population: randomized patients, patients in the safety population, patients in Intent-to-Treat population, patients in Per-Protocol population, patients who completed the study (including follow-up), patients who discontinued early, patients who completed study treatment, patients who discontinued study treatment early also presented by reason for early discontinuation and study duration in days. The denominators will be the number of randomized patients. A Kaplan-Meier plot of time to discontinuation of study treatment will be presented by treatment for the ITT population.

Completion/discontinuation status, inclusion/exclusion criteria definitions and Inclusion/exclusion criteria violations will be listed by patient.

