### 12.1. Adverse Events

AEs for all patients in the safety population will be included in the AE summaries.

Adverse events will be summarized by system organ class (SOC) and preferred term (PT) for each treatment and Orismilast total, based on the MedDRA dictionary version 24.0. Severity of AEs will be graded according to National Cancer Institute (NCI) Common Terminology Criteria for Adverse Events (CTCAE) version 5.

Any AEs that occur before dosing on study Baseline will be categorized as pretreatment events. TEAEs will be defined as those AEs that occur or worsen in severity after initial dosing and up to 7 days after the last dose of study drug.

Duration will be calculated for AEs that resolve as the difference between the resolution date and onset date plus 1 and expressed in days.

The summary tables will include the number of patients and the number of events. Percentages will be based on the number of patients in the safety population. For summaries by SOC and PT, a patient will be counted once at the SOC level and once at each PT within the SOC level.

For summaries by SOC, PT, and maximum severity, a patient will be counted once at the highest severity level for which the event occurred at the SOC level and the highest severity level for each unique PT within that SOC level. Therefore, patients may only contribute once to each PT and once to each SOC level.

The summaries presenting frequency of AEs by SOC and PT will be ordered by Orismilast total descending frequency of SOC and then, within a SOC, by Orismilast total descending frequency of PT.

The following tables will be provided:

- An overall summary of the number of events and number and percentage of patients reporting TEAEs, related TEAEs (TEAEs recorded as “Relationship to study drug” = “Possibly” or “Probably” or “Definitely”), serious TEAEs (TESAEs), TEAEs resulting in death, TEAEs of special interest, TEAEs leading to study drug discontinuation, TESAEs leading to study drug discontinuation, TEAEs by relationship and TEAEs by toxicity grade;
- TEAEs overall by system organ class and preferred term;

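### Follow-up AE and SAE percentages are based on every dosed patient, so anyone not observed after the last dose is counted as having had no event

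*SAP*

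**What the plan says.** SAP 12.1 ends its list of AE tables with "AEs starting in the 4-week Follow-up period overall by system organ class and preferred term" and the equivalent for SAEs. One rule in the same section sets the base for all AE summary tables: "Percentages will be based on the number of patients in the safety population". SAP 6.2 defines that population: "The safety population will include all randomized patients who receive at least 1 dose of the study drug". Nothing in it requires that the patient was seen after treatment. SAP 18 carries the two tables as 14.3.1.18 ("Adverse Events Starting in the 4-week Follow-up Period by System Organ Class and Preferred Term") and 14.3.1.19 ("Serious Adverse Events Starting in the 4-week Follow-up Period by System Organ Class and Preferred Term"), both assigned to the safety population. No number at risk, person-time or exposure-adjusted rate is planned for them. SAP 7.2 defines the treatment period; the follow-up period is not defined.

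The protocol lists ways to leave the study without further contact: withdrawal of consent, and "lost to Follow up: the patient stopped coming for visits, and study personnel were unable to contact the patient" (Section 8.4). Patients who only stop the drug, however, are to be kept in the study for safety evaluation (Sections 8.4 and 9.3). The Follow-up visit is timed four weeks after treatment ends, whether by completion or by discontinuation (Section 7.1), and AEs are collected up to that visit (Section 12.9.1). For SAEs, Section 12.9.4 says that an event "within 30 days of stopping the treatment must be reported".

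**The concern.** A percentage of patients with an event in a given period should rest on patients in whom an event in that period could have been recorded. Here the numerator can come only from patients about whom something was learned after the last dose, while the denominator includes everyone dosed. A patient who attends the Week 16 visit and is never heard from again is counted in the same way as one who attends Week 20 and reports nothing.

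The two tables carry some weight. Under SAP 12.1 an AE is treatment-emergent only up to 7 days after the last dose, while the safety endpoint in SAP 5.5 covers the four-week follow-up as well. An event starting on day 8 or later after the last dose therefore reaches a summary table only through these two. The trial is also meant to identify the dose with the best benefit/risk ratio, so a reader will compare these columns across arms.

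**Working it through.** **Inputs from the documents.** Base: all dosed patients (SAP 6.2, 12.1, 18). Arm size: about 50 (SAP 4.3).

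**Inputs not in the documents (assumed).** f, the share of dosed patients with no observation after the last dose: 0% to 50%. r, the true risk of an AE starting in follow-up: 5%, 10% and 20%.

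**Plan's own figure.** The documents state no follow-up AE rate. The only related figure is the arm size, which reproduces: difference 50.9 − 32.2 = 18.7 points, SD 33, 50 per arm, two-sided 5% t-test gives power 0.801 against the stated 80%. The argument below uses this only as the N.

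**Step 1, one arm.** Of N dosed patients, (1 − f)N are observed and r(1 − f)N are expected to have an event, if being unobserved is unrelated to risk.

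- SAP base: r(1 − f)N / N = r(1 − f)
- Observed base: r(1 − f)N / [(1 − f)N] = r

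With N = 50 and r = 10%:

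| f | observed | expected with event | % on SAP base | % on observed base |
|---|---|---|---|---|
| 0% | 50 | 5.0 | 10.0 | 10.0 |
| 5% | 47.5 | 4.75 | 9.5 | 10.0 |
| 10% | 45 | 4.5 | 9.0 | 10.0 |
| 20% | 40 | 4.0 | 8.0 | 10.0 |
| 30% | 35 | 3.5 | 7.0 | 10.0 |
| 50% | 25 | 2.5 | 5.0 | 10.0 |

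The relative understatement equals f whatever r is: at f = 30%, 5% prints as 3.5% and 20% as 14.0%.

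**Step 2, two arms with equal true risk.** Printed ratio, active to placebo = (1 − f_active) / (1 − f_placebo).

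- 30% against 10% unobserved: 0.70 / 0.90 = 0.78 (7.0% against 9.0%)
- 30% against 5%: 0.70 / 0.95 = 0.74 (7.0% against 9.5%)
- 50% against 50%: 0.50 / 0.50 = 1.00 (5.0% in both)

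Unequal shares distort the comparison; equal shares lower both columns and leave the ratio intact.

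**Step 3, size in patients.** At 50 per arm, 7.0% against 9.0% is 3.5 against 4.5 expected patients: one patient.

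**Step 4, SAE window.** Four weeks is 28 days and SAE collection runs to 30, a gap of 2 days. The Week 20 visit has a window of ±3 days (Protocol Table 4), so a follow-up period that ends at the visit can reach about day 31. The SAP gives no day count that would settle which applies.

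**The case against.** A reader might infer that the higher doses will look safer than they are because more of their patients stop for intolerance. The documents do not support that. Patients who stop the drug are to be followed for safety, with a visit four weeks later, so they are not the unobserved group; only leaving the study without later contact matters. The Phase 2a trial does not establish a difference either. AE withdrawals were 50% on orismilast and 16.7% on placebo, but all-cause withdrawal was about half in both groups. That trial also used the immediate-release tablet, and Protocol 5.3 expects better tolerability from the present formulation. Withdrawal is in any case not the same quantity as f. This part of the objection stands in full.

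Three further points soften the problem without removing it.

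- Early leavers are asked back within four weeks of the last dose, and SAEs are reportable for 30 days, so some are partly observed. The factor (1 − f) applies only to those with no observation at all.
- Event and patient counts are shown, follow-up AEs and all SAEs are listed by patient, and the disposition table counts study completers with follow-up included. A reader can correct the percentages roughly, though completers are not the same set as patients observed at some time after the last dose.
- Safety analysis is descriptive, so no test or decision rule uses these percentages.

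A changed denominator has its own weakness. If any contact qualifies, an event report can itself admit a patient to the base. Suppose 40 of 50 are seen with 4 events (4/40 = 10.0%) and one unseen patient is known only through an SAE report. The at-risk figure becomes 5/41 = 12.2%, while the safety-population figure is 5/50 = 10.0%. For that reason the base should rest on scheduled ascertainment, and both Ns should be shown.

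**Conclusion.** The concern holds as a minor defect of presentation. Within each arm, the percentages in Tables 14.3.1.18 and 14.3.1.19 are too low by the share of that arm not observed after the last dose. This follows from the SAP's stated base, provided that unobserved patients have the same risk as observed ones. The amount cannot be calculated, because neither f nor r is given; over the assumed range of f from 5% to 30%, a true 10% prints as 9.5% down to 7.0%. A bias between arms is possible but not shown, and no direction in favour of any dose can be claimed.

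Two drafting matters belong with it. SAP 12.1 restricts summary tables to treatment-emergent events, which end 7 days after the last dose, yet lists two tables of events starting over a four-week follow-up. And the SAE table's four weeks do not match the protocol's 30 days; this concerns about two days, with the SAEs listed in any case, so it is a consistency point only.

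**What to change.** In the SAP:

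1. Define the follow-up period in Section 7.2 by days from the last dose.
2. In Section 12.1, for Tables 14.3.1.18 and 14.3.1.19 only, use as column N and percentage base the safety-population patients who entered follow-up. These are patients whose AE status was ascertained at a visit or scheduled contact after the last dose, plus any patient with a reported post-treatment AE or SAE, so that every patient in the numerator is also in the base. Show the safety-population N alongside, per arm, and footnote how many entered only through an event report.
3. Reword the sentence limiting summary tables to treatment-emergent events so that it excepts these two tables.
4. Align the SAE table window with the 30-day collection in Protocol 12.9.4.

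The cost is a few SAP sentences, one derived flag, and a footnote explaining why N differs from the other AE tables. The flag must be derived from visit, contact and AE records, since the planned completer count does not identify the same patients. The revised percentage is unbiased only if missing follow-up is unrelated to risk, and a single early contact does not amount to four weeks observed. Showing both Ns lets the reader judge how much depends on this.
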